5.3.1.1 Terms and volume of data on the excluded subjects

In case of trial discontinuation on the subject's free will, the Investigator should make effort to find out the reason thereof. In case of trial discontinuation due to AEs/SAEs, the subject should be followed-up until the AEs/SAEs are resolved. In case of discontinuation from the trial prematurely, the patient should visit the trial site for early discontinuation procedures (as an unscheduled visit); if the patient refuses to visit the trial site, he/she should be contacted by phone with recording of all available information.

5.3.2 Terms and conditions of suspend or discontinuation of the trial therapy

The patients may stop taking the study drugs according to the protocol or upon withdrawal from the trial.

5.3.3 Replacement of the excluded subjects

Replacement of the excluded patients during the trial is not envisaged.

5.4 Acceptable contraception methods

The patients must follow adequate contraceptive methods throughout the trial as well as within 30 days after its completion.

Effective contraception methods include:

- True abstinence;
- Oral contraceptives (combination drugs containing progestogen, or progestogen alone);
- Injectable progestogen;
- Levonorgestrel implants;
- Estrogen-containing vaginal ring;
- Transdermal contraceptive patches;
- Intrauterine device (IUD) or intrauterine system (IUS) meeting the efficacy criteria according to Prescribing Information;
- A male partner has been sterile (vasectomy with documented azoospermia) prior to inclusion of a woman, provided that he is the only partner of the female patient. For the purpose of this definition, "documented" is related to the result of a patient's medical examination by the Investigator/responsible person or a patient's past medical history review for evaluation of eligibility for

- inclusion, obtained during the interview with a patient or from his/her medical records.
- Double barrier method: a condom or an occlusive cap (diaphragm or cervical/vault caps) with a spermicide (foam/gel/film/cream/suppository).

Men should use adequate contraception during the trial, since signing of the Informed Consent Form and till the trial completion, and for 30 days after the trial completion.

6 Trial therapy

6.1 Therapy regimens

The study drug group: Angal S, topical spray [menthol], 0.5 mg + 2 mg/1 ml, will be used according to Prescribing Information in the following way: 3 to 5 consecutive presses on the actuator button, 6 to 10 times per day, for 4 days or until full recovery (TSS ≤ 2), whichever occurs first during 4 days of therapy. One dose of Angal S is 3 to 5 consecutive presses.

The comparator drug group: ANTI-ANGIN® FORMULA, topical metered spray, 0.12 mg + 0.24 mg/dose, will be used according to Prescribing Information in the following way: 1 to 2 consecutive presses on the actuator button, up to 6 times per day, for 5 days or until full recovery (TSS \leq 2), whichever occurs first during 5 days of therapy. One dose of ANTI-ANGIN® FORMULA is 1–2 sprays.

6.2 Allowed and prohibited therapy

6.2.1 Allowed prior and concomitant therapy

All concomitant therapies except for those stated in Section 6.2.2 are allowed.

6.2.2 Prohibited prior and concomitant therapy

The drugs listed below are prohibited for use throughout the trial period:

- 1. Topical drugs (aerosols, sprays, inhalations, gargle solutions, fast-disintegrating tablets/lozenges/pastilles) in the pharynx or nose.
- 2. Systemic, inhalation, or nasal glucocorticosteroids.
- 3. Systemic or topical (intranasal or pharyngeal) antibacterial drugs.
- 4. Anti-viral drugs.
- 5. Immunomodulatory agents.
- 6. Painkillers or antipyretic agents.
- 7. Class I antiarrhythmics.
- 8. Cholinesterase inhibitors (including neostigmine, distigmine, pyridostigmine) and other drugs for myasthenia.

6.3 Methods to monitor the subjects' compliance with trial procedures

At every visit after Visit 1, the subjects' compliance will be checked by counting the unused drug and analysis of the patient's diaries.

The protocol envisages the dose of Angal S, the study drug, as 3 to 5 consecutive presses on the actuator button, 6 to 10 times per day, and ANTI-ANGIN® FORMULA, the comparator drug, 1–2 sprays up to 6 times per day with not less than a 2-hour intervals between the doses. Both drugs should be taken when needed (a sore throat).

In view of the nature of drug intake (when needed), the lower margin of compliance will not be evaluated; the number of used doses is compared to maximum amounts stated in the protocol for the study drug (up to 5 sprays at once, not more than 10 times per day for Angal) or Prescribing Information for the comparator drug (up to 2 sprays at once, not more than 6 times per day for ANTI-ANGIN® FORMULA).

List of efficacy parameters

7 Efficacy evaluation

Primary outcome measure

7.1

The primary outcome measure was the percentage of patients without sore throat after 3 days of therapy, as evaluated by the Investigator according to the Tonsillopharyngitis Severity Score (TSS), in both Angal S and ANTI-ANGIN® FORMULA arms.

Secondary outcome measures

The secondary outcome measures in both therapy groups were:

- Frequency of ≥50% total score reduction according to the TSS questionnaire completed by the Investigator as compared to the baseline in both Angal S and ANTI-ANGIN® FORMULA groups at Visit 2 (Day 4).
- Total score reduction according to the TSS questionnaire, as well as a reduction in the symptoms (sore throat, difficulty in swallowing, salivation, erythema, and fever) after a 3-day therapy, at Visit 2 (Day 4), as compared to the baseline total score.
- A period of time required for disease symptoms relief, determined according to the patient's diary (subjective patient's evaluation), but no more than 5 days during the trial—for patients who have achieved the corresponding outcome.
- A proportion (%) of patients who fully recovered by Day 4 in Group A and by Day 5 in Group B (the outcome of a disease according to the objective evaluation by the Investigator, the total score according to the TSS questionnaire ≤2).
- A change in the sore throat intensity by 100 mm VAS (visual analogue scale filled in by the patient) at the beginning, after 3 days of therapy, and at the end of treatment in both groups.

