4.4.4 Strength and dosage regimen of the study drugs

Angal S, topical spray [menthol], 0.5 mg + 2 mg/1 ml (Sandoz d.d., Slovenia), the study drug, will be used according to Prescribing Information in the following way: 3 to 5 consecutive presses on the actuator button, 6 to 10 times per day, for 4 days or until full recovery (TSS \leq 2), whichever occurs first during 4 days of therapy. One dose of Angal S is 3 to 5 consecutive presses.

ANTI-ANGIN® FORMULA, topical metered spray, 0.12 mg + 0.24 mg/dose (OOO Valeant, Russia), the comparator drug, will be used according to Prescribing Information in the following way: 1 to 2 consecutive presses on the actuator button, up to 6 times per day, for 5 days or until full recovery (TSS \leq 2), whichever occurs first during 5 days of therapy. One dose of ANTI-ANGIN® FORMULA is 1–2 sprays.

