5.3 Exclusion criteria

5.3.1 Terms and conditions for the subjects' exclusion from the trial

The subjects may be excluded from the trial on their own free will at any moment, without giving any reason, as well as upon decision of the Investigator or Sponsor in cases when continuation of the participation may inflict harm to the patient's health and/or life. In addition, the patient must be excluded in the cases listed below:

- 1. Negative course of the disease with signs of the secondary bacterial infection (including body temperature increase above 37.5 °C).
- 2. The Ethics Committee, regulatory authorities, or Sponsor terminate the trial or participation of the specific trial site for any reason.
- 3. The Investigator's decision to withdraw the patient from the trial in the interests of the patient.
- 4. Withdrawal of the informed consent (unwillingness of the patient to continue his/her participation in the trial).
- 5. Serious deviation from the trial protocol.
- 6. Individual intolerance of the study drugs.
- 7. Clinically significant adverse event or serious adverse event.
- 8. Patient's non-compliance.
- 9. False inclusion (e.g., the patient was included in breach of the inclusion/non-inclusion criteria).
- 10. The patient complies with the non-inclusion criteria during the trial.
- 11. The patient receives or requires an additional therapy which might influence the trial results or patient's safety (see *Prohibited concomitant therapy* section).

12. Other conditions or events which, in the Investigator's opinion, require the patient's exclusion from the trial.

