16.3 Appendix 3. The patient's diary

TE_003_ANG_LSP	THE PATIENT'S DIARY	PATIENT No

PATIENT COUNSELING INFORMATION

DEAR PATIENT,

This is a patient's diary. Please read the instructions for filling-in carefully. In case of any questions, feel free to ask the Investigator.

You are participating in a clinical trial of efficacy and safety of Angal S, spray with a menthol taste, compared to ANTI-ANGIN® FORMULA, a similar drug by action and composition, for therapy of acute, uncomplicated throat conditions.

The Investigator, based on your complaints and objective examination, has revealed that you have an acute, uncomplicated, infectious and inflammatory disease of the throat. One of the study drugs is prescribed to you to treat your condition: Angal S, spray with a menthol taste, or ANTI-ANGIN® FORMULA, spray. Both you and the Investigator know which drug you are taking because this is an open (unblinded) trial. The information you are going to note in this diary is very important for this trial; therefore, please enter the data without corrections.

Fill in the patient's diary every day. Encircle the answers YES or NO according to your opinion: YES. Take the diary with you when you visit the trial site. You will enter the following data:

- 1. Study drug use: every time when you use a spray dose, record the time and briefly describe your complaints at that moment. Specify if you had a pain in your throat before the spray use or not.
- 2. Measurement of body temperature: measure your body temperature 3 times a day or more frequently if needed. Specify a time and result of the measurement. Measure your body temperature in the axillary cavity, in a sitting position for 5 minutes. Please inform the Investigator on changes in your well-being.
- 3. Course of the disease: specify if you noted any changes based on your subjective evaluation of the disease signs.

If you feel worsening of state, increase of body temperature, aggravation of pain in your throat, contact the Investigator by the phone_____! If necessary, the Investigator will invite you for an unscheduled visit to the trial site for additional examination and therapy correction.

PRESCRIBING INFORMATION FOR THE STUDY DRUG

Angal, topical spray, one dose includes 3 to 5 consecutive presses on the actuator button, six to ten times per day, for not more than 4 days.

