ANTI-ANGIN® FORMULA, topical spray, one dose includes 1 to 2 consecutive presses on the actuator button, up to 6 times per day, for not more than 5 days.

TE_003_ANG_LSP	THE PATIENT'S DIARY	PATIENT No

DAY 1: DD/MM/YYYY

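### Section 6.3 makes both sprays as-needed and adds a 2-hour interval; neither appears in the regimen sections or the diary, and as-needed use conflicts with the Angal S floor of six uses a day

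*Protocol*

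**What the plan says.** The regimen is given in the protocol synopsis and in sections 2.4, 3.2, 4.4.4 and 6.1. For Group A, 4.4.4 reads "3 to 5 consecutive presses on the actuator button, 6 to 10 times per day, for 4 days", or until full recovery if sooner. For Group B, 6.1 reads "1 to 2 consecutive presses on the actuator button, up to 6 times per day". SAP 3.1 gives the same frequencies.

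The diary (Appendix 3) tells Group A patients "one dose includes 3 to 5 consecutive presses on the actuator button, six to ten times per day, for not more than 4 days" and Group B patients "one dose includes 1 to 2 consecutive presses on the actuator button, up to 6 times per day, for not more than 5 days". None of these texts sets a minimum interval or says that use depends on pain.

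Section 6.3 restates both frequencies and then continues "with not less than a 2-hour intervals between the doses. Both drugs should be taken when needed (a sore throat"). Because use is as needed, it says that "the lower margin of compliance will not be evaluated; the number of used doses is compared to maximum amounts stated in the protocol" (for Angal S) or in the Prescribing Information (for the comparator). The Angal S maximum is 5 sprays at once, 10 times a day.

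Section 5.3.1 lists "Patient's non-compliance" among the cases in which a patient must be excluded, without defining it. The synopsis version of that list says that patients may be excluded.

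**The concern.** A frequency with a lower limit and an instruction to dose only for pain are different regimens. Section 6.3 contains both, and everything else written for sites and patients contains only the first. The mismatch falls on the test arm: six is a minimum for Angal S and a maximum for the comparator.

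The interval adds a second uncertainty. It appears once, directly after the comparator's regimen and just before a sentence about both drugs, so a site could apply it to one spray or to both.

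At stake is consistency of treatment. Investigators train patients at Visit 1. One site could teach at least six uses a day, another use for pain only, and a third either of these with 2-hour spacing. Angal S exposure over the three days before the primary assessment could then depend on the site's reading. The trial is open-label with a non-inferiority objective, so what the test arm was told to take should be unambiguous.

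**Working it through.** The plan states no figure on this point to reproduce. The check compares the texts and then applies simple arithmetic.

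**Step 1. The texts side by side.**

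| Place | Group A uses/day | Group B uses/day | Interval | As needed |
|---|---|---|---|---|
| Synopsis; 2.4; 3.2; 4.4.4; 6.1 | 6–10 | up to 6 | none | no |
| SAP 3.1 | 6–10 | up to 6 | none | no |
| Diary, Appendix 3 | 6–10 | up to 6 | none | no |
| 6.3 | 6–10 | up to 6 | at least 2 h; which drug is unclear | yes, both |

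The product descriptions in 2.1.1 and 2.1.2 give no interval between doses either.

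**Step 2. The as-needed conflict.** This step needs no assumption about hours.

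- Group A, regimen text: minimum 6 × 3 = 18 presses a day, maximum 10 × 5 = 50.
- Group A, as needed: 0 on a day without pain.
- Group B, either reading: 0 to 6 × 2 = 12 presses a day.

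Stopping at full recovery does not remove the conflict. Sections 4.4.4 and 6.1 define recovery as total TSS ≤ 2, and absence of pain is a different state. A patient scoring 0 for sore throat and 1 each for swallowing, salivation and hyperemia totals 3 and has not recovered. The investigator completes the TSS at site visits, and none is scheduled on Days 2 and 3.

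**Step 3. The interval, if it covers both drugs.** For n uses at least 2 h apart, the shortest span from first to last is (n − 1) × 2 h.

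- Group A at 10 uses: 9 × 2 = 18 h.
- Group B at 6 uses: 5 × 2 = 10 h.

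The most uses that fit in a window of W hours is floor(W/2) + 1. The documents give no daily window, so W is an assumption:

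| W (h) | Most uses | Mean gap at 10 uses (h) | Mean gap at 6 uses (h) |
|---|---|---|---|
| 14 | 8 | 14/9 = 1.56 | 14/5 = 2.8 |
| 16 | 9 | 16/9 = 1.78 | 16/5 = 3.2 |
| 17 | 9 | 17/9 = 1.89 | 17/5 = 3.4 |
| 18 | 10 | 18/9 = 2.0 | 18/5 = 3.6 |

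In a 16-hour window the attainable Group A maximum is 9 × 5 = 45 presses, against 50 in the diary. On Day 1 the first dose is taken at the site (4.2.4.1). If that is between 08:00 and 12:00 (also assumed), 7 to 9 uses fit before midnight.

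**Step 4. The interval, if it covers the comparator only.** The limit on 10 uses of Angal S disappears. The conflict in step 2 remains, and the Group B diary still omits the interval.

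**The case against.** The strongest reply is that 6.3 is a compliance section and tests little. It waives the lower limit and compares the number of doses with a maximum. The diary asks about pain before each use and, three times a day, whether the spray is still needed. Section 2.1.1 limits the period of use to what relieves pain or irritation. All of this suits symptom-led use, and the interval clause reads naturally as part of the comparator's regimen.

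Much of that stands, and it rules out three stronger inferences a reader might draw.

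- *A Group A patient at 10 uses a day necessarily breaches 6.3.* This requires the interval to cover Angal S and all doses to fall within less than 18 h. The documents establish neither. Such a patient meets the only numerical check in 6.3.
- *Patients who follow the diary will be excluded, and only in Group A.* No text links spacing to the non-compliance item in 5.3.1, and SAP 3.2 does not list it among serious deviations. The diary records clock times and non-compliance is undefined, so exclusion for spacing is possible, but it is not a stated check. Group B patients can also cluster doses, and their diary gives no interval either.
- *Patients have only the diary to go by.* They are also trained at the site, take the first dose under supervision and receive an information sheet that is not in the reviewed text.

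The reply does not remove the conflict in the instruction itself. Waiving a check on the lower limit does not tell a pain-free patient whether to take six doses or none. The diary questions record pain and perceived need, but the printed instruction beside them still has a floor of six.

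**Conclusion.** The point holds as a conflict in the dosing instruction, mainly for the test arm. Section 6.3 alone makes use as-needed, and this contradicts the Group A floor found in every regimen text and in 6.3 itself. The size is 18 presses against 0 on a pain-free day before recovery, with no assumption about waking hours.

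The interval is a second, conditional defect. It is missing everywhere else, and its scope is unclear. If it covers both drugs, 10 Angal S uses need at least 18 h and 6 comparator uses need 10 h. The loss is then modest: one use a day in an assumed 16-hour window and two in 14 h. If it covers the comparator only, this part reduces to an instruction missing from the comparator's regimen text and diary.

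Variation in exposure between sites is a plausible consequence; the documents do not show its extent. The point does not depend on the SAP 3.2 rule removing patients who miss more than 3 doses from the PP set, though what counts as missed also depends on which instruction applies. A correction should be made. Which dosing rule is right is for the sponsor to decide.

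**What to change.** Reconcile 6.3 with the synopsis, 2.4, 3.2, 4.4.4, 6.1, SAP 3.1 and Appendix 3 so that one instruction stands for each arm. It should state the frequency, whether use is scheduled or as needed, and whether an interval applies and to which drug. The sponsor decides which version holds.

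Print that same text in the diary and use it for site training. State in 6.3 and SAP 3.2 that use in line with the reconciled instruction is neither non-compliance nor a protocol deviation.

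The cost is a wording amendment to the protocol and SAP and a reprinted diary page. No procedures or patients are added.

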7.2 Methods and timing for evaluation, recording, and analysis of efficacy parameters

The methods for efficacy criteria evaluation are described in Section 4.2.3.2. The first endpoint is evaluated in the morning at Visit 2 (Day 4, after 3 days of the trial therapy) before the study drugs intake. Other efficacy endpoints are evaluated in terms stated in Section 7.1.

8 Safety evaluation

8.1 List of safety parameters

The following parameters will be taken into account for the safety evaluation:

- AEs and/or SAEs rates per trial arms;
- Global tolerance evaluation during the trial by the Investigator and patient;
- Vital signs (heart rate, blood pressure, body temperature, breathing rate);
- ECG parameters;
- Laboratory results.

8.2 Methods and timing for evaluation, recording, and analysis of safety parameters

Safety parameters are evaluated at every planned and unscheduled visit.

8.3 Requirements for reporting, registration, and reporting of AEs and intercurrent diseases

8.3.1 Definitions of adverse events and serious adverse events

Adverse event (AE) is any adverse medical event identified in a patient or a clinical trial patient after the use of the drug, which may or may not have a causal relationship with its usage. Thus, adverse event (AE) can represent any adverse symptom (including laboratory deviation from the norm), complaint, or disease, for which a temporal causal relation cannot be excluded with the application of medicinal (investigational) product, regardless of the presence or absence of such a relation.

Serious adverse event (SAE) represents any event, unfavorable from medical perspective, which with any dose:

- Resulted in death;
- Is life threatening;
- Results in disability/incapacity to work;
- Is a congenital anomaly or development defect;
- Requires hospitalization or its extension;
- significant from medical perspective: a decision whether expedited reports are feasible in other situations (e.g., in case of events important from medical perspective, which not directly life-threatening are

for a patient, do not result in death or hospitalization, but pose the patient to risk, or require intervention to prevent one of the above outcomes) shall be made on the basis of medical and scientific evaluation. Such cases should be usually considered serious adverse events.

Adverse drug reaction (ADR) is any adverse event which might have causal relation to the drug in the opinion of the Investigator or Sponsor (see Section 8.3.3 below).

An unexpected adverse reaction is defined as an adverse drug reaction, the nature or severity of which is not consistent with the Reference Safety Information (e.g., SmPC, Investigator's Brochure). The term "severity" is used to describe the intensity of a specific event. This term should be distinguished from the term "serious". Reports which add significant information on specificity, increase in incidence, or severity of the known, already documented serious adverse reactions, constitute the unforeseen events.

Information about side effects already known for this study drug is available in the Investigator's Brochure. This information will be included into Patient Information Sheet, and it should be discussed with the trial subjects.

More details are given in Brief Reference Manual for filling in the Serious Adverse Event Report Form (to be provided by the Sponsor).

8.3.2 Intensity of AE

The term "severity" is used to describe the intensity of a specific event. This term should be distinguished from the term "serious". During the trial, the Investigator will detect adverse events and classify them by intensity as follows:

- Mild event: as a rule, is temporary and does not restrict normal daily activities;
- Moderate event: restricts normal daily activities significantly;
- Severe event: impedes normal daily activities in full.

8.3.3 Causality with the study drug

The Investigator will perform evaluation of adverse events after examination of all available data. In addition, he/she will perform their repeated evaluation if new information appears. The study drug is the drug investigated during the trial, and control drug or placebo used during any phase of this trial.

All AEs spontaneously reported by volunteers or observed by the Investigator will be evaluated in accordance with the following definitions:

Suspected: temporary relation between development of clinical event and the used study drug indicates for the **possible presence of causality,** while other drugs, therapeutic interventions, or baseline states do not allow explaining development of this event with sufficient grounds.

Non-suspected: temporary relation between development of clinical event and used study drug **indicates for the remote presence of causality**, while other drugs, therapeutic interventions, or baseline states can be considered with sufficient grounds as explanation for observed event.

Evaluation of causality is of great significance, and it should be performed for each reported unique event and for each study drug, not being the study drug or any other concomitant drug (if appropriate). In case of no evaluation of causality available, the Sponsor will consider such events as associated with the trial therapy.

The Investigator must inform LPPV on AEs with suspected causality to the drug which is not a study drug or another concomitant drug (produced by Sandoz or other manufacturers), even if those AEs are not serious (see Section 8.3.5 for contact information).

